### **Background and Rationale**

Attention Deficit and Hyperactivity Disorder (ADHD) is a multifactorial neurodevelopmental disorder characterized by attention deficits, impulsivity, and hyperactivity. This study investigates the effect of music-based occupational therapy on attention and executive functions in children with ADHD. Music-based rhythmic and motor activities are hypothesized to enhance cognitive, emotional, and behavioral regulation.

### **Objectives**

#### **Primary Objective:**

To examine the effect of music-based occupational therapy on attention performance in children with ADHD.

#### **Secondary Objective:**

To evaluate the effects of the intervention on executive function skills and caregiver burden.

## **Study Design**

**Design Type:** Experimental, two-arm parallel design

### **Groups:**

- Group 1: Music-Based Occupational Therapy
- Group 2: Standard Occupational Therapy (Control)

**Randomization:** Simple random assignment

**Masking:** None (Open Label)

**Duration:** 6 weeks, 1 session per week, 45 minutes each

**Setting:** Istanbul Medipol University, Department of Occupational Therapy

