## **Outcome Measures**

#### **Primary Outcome:**

- Change in attention (DSM-V Level 2 Inattention Scale)

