#### **Secondary Outcomes:**

- Executive Function (Childhood Executive Function Inventory)
- Caregiver Burden (Zarit Burden Scale)

All measures assessed pre- and post-intervention.

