## **Data Analysis Plan**

The analyses were performed using SPSS 25.0 software. For descriptive statistics, mean, standard deviation, and percentage values were used. Normal distribution was checked with the Kolmogorov-Smirnov Test. For independent variables, nominal data were evaluated with the Chi-Square Test, while numerical data were assessed with the T-Test / Mann-Whitney U Test. Two-Way Repeated Measures ANOVA was applied for within-group and between-group time interactions. The significance level for all tests was accepted as  $p < 0.05$ .

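### Simple randomisation of children aged 5 to 12, with no covariate in any stated analysis, leaves chance age imbalance unhandled: a cost in precision, not a bias

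*Combined protocol and SAP*

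**What the plan says.** Under Study Design the trial is described as "Experimental, two-arm parallel design". Under Groups, allocation is given as "Simple random assignment", without masking, in one university department. No blocks, strata, minimisation, allocation ratio or target arm size appears anywhere. That there is no restriction is inferred from the word simple and from this silence; the protocol does not say so outright.

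The Inclusion Criteria admit children from 5 to 12 years as a single group. The primary outcome is "Change in attention (DSM-V Level 2 Inattention Scale", and the Secondary Outcomes section adds "All measures assessed pre- and post-intervention".

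The Data Analysis Plan states that "Two-Way Repeated Measures ANOVA was applied for within-group and between-group time interactions". It also says that "nominal data were evaluated with the Chi-Square Test, while numerical data were assessed with the T-Test / Mann-Whitney U Test". It names no covariate, no regression or ANCOVA, and no age subgroup. It does not say which test decides the primary outcome.

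**The concern.** Eight years of age are pooled, and the allocation method does nothing to keep the arms alike in age. If age is related to how much a child changes over the six weeks, or to how well the child responds, a chance age gap moves the estimated treatment difference in one direction or the other. Nothing in the stated analysis takes that movement out again.

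Two things are at stake. One is precision: variation in change that age could explain stays in the error term. The other is interpretation: if the baseline table shows an age gap, the plan has no prespecified way to allow for it, and an adjustment chosen after seeing the gap would be data-driven, in a trial that is also unmasked.

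**Working it through.** **Inputs from the documents.** Two parallel arms; simple assignment; ages 5 to 12; two assessments; primary outcome a pre-post change; no covariate. The plan gives no sample size, power, effect size, SD or allocation ratio, so it has no figure to reproduce.

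**Assumptions.** 1:1 coin-flip allocation; whole-year ages spread evenly over 5 to 12; total N from 20 to 100; correlation r between age and the analysed change of 0.2 to 0.4.

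**Step 1: what the primary contrast is.** With two time points, the group-by-time term of a two-way repeated measures ANOVA is the between-arm comparison of change. Stable age differences in level cancel. So r must be the correlation of age with six-week change (or, in an ANCOVA, with the post score given baseline), not with attention level.

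**Step 2: spread of age.** SD(age) = √((8² − 1)/12) = √5.25 = 2.29 years.

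**Step 3: how often the arms differ in mean age.** With near-equal arms the SD of the difference in mean age is about 2 × 2.29/√N; for N = 40 this is 4.58/6.32 = 0.72 years. A simulation of 200,000 trials per N, which lets arm sizes vary, gives slightly more:

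| Assumed total N | SD of age difference (years) | Chance of a gap of 1 year or more |
|---|---|---|
| 20 | 1.05 | 35% |
| 30 | 0.85 | 25% |
| 40 | 0.74 | 18% |
| 60 | 0.60 | 9% |
| 80 | 0.52 | 5% |
| 100 | 0.46 | 3% |

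**Step 4: what a 1-year gap does.** Shift in the contrast, in outcome SD, = r × 1/SD(age):

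- r = 0.2: 0.2/2.29 = 0.09
- r = 0.3: 0.3/2.29 = 0.13
- r = 0.4: 0.4/2.29 = 0.17

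**Step 5: the shift against sampling error.** With outcome SD 1 and equal arms, the standard error of the contrast is 2/√N, or 0.37 / 0.32 / 0.26 for N = 30 / 40 / 60. A shift of 0.13 is then about 0.36 / 0.41 / 0.50 standard errors.

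**Step 6: what adjustment gains.** Residual variance is multiplied by 1 − r²: 0.96, 0.91 and 0.84 for r = 0.2, 0.3 and 0.4.

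**Step 7: arm sizes.** Information relative to equal arms is 4 × n₁ × n₂/N². For 60:40 this is 4 × 0.6 × 0.4 = 0.96. A split at least that uneven has exact binomial probability 36% / 27% / 16% for N = 30 / 40 / 60, but it costs only 4% of the information when it is exactly 60:40.

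**The case against.** The strongest reply is that simple randomisation is a valid method. It favours neither arm, and the test's type I error already allows for chance imbalance in age and everything else. A reader might infer that the missing age term biases the trial or invalidates its p-value. The documents do not support that, and this part of the reply stands in full.

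The second reply is that the primary outcome is change, so the familiar fact that older and younger children differ in attention level is beside the point. This stands for stable differences in level. It does not dispose of age-related differences in change or response. Nor does it cover the t-test / Mann-Whitney comparisons if those are applied to post-intervention scores, which the plan leaves unclear; there a difference in level would carry through. The documents give no value for the correlation of age with change, and it is probably smaller than the correlation with level, so 0.2 to 0.4 should be read as an upper-end range.

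Third, nothing in the text says that the trial is small. A single department makes that plausible but does not establish it, and at 100 children the concern has nearly gone.

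Fourth, a reader might infer that uneven arm sizes are a serious fault of simple assignment. They are not: a 60:40 split keeps 96% of the information.

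Finally, the Data Analysis Plan and Ethical Considerations are written in the past tense, so allocation may be complete. That limits what can be changed in the design but not in the analysis.

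**Conclusion.** The point holds in a limited form. Age is controlled neither by the allocation nor by any stated analysis. The consequence is a modest loss of precision and, in some trials, a conditional imbalance that the stated analysis cannot remove; it is not a systematic error.

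The size depends on two quantities that the documents do not give. On assumed totals, the concern matters below about 60 children and fades by 100. Where a gap of a full year arises, the shift is on the assumed correlations less than one fifth of an outcome SD, and at r = 0.3 at most half a standard error for totals of 30 to 60. The case for acting rests less on the size of the harm than on how little the remedy costs: age must already be recorded to establish eligibility.

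**What to change.** In the Data Analysis Plan, state that the between-group analysis of the inattention and executive function outcomes is an ANCOVA of the post-intervention score on group, baseline score and age in years as a continuous term. Compared with an unadjusted comparison of change, this uses two more degrees of freedom (one if baseline is already in the model) and needs no new data. The argument above does not extend to caregiver burden, so age need not be added there on this ground. If anyone has already seen outcome data, keep the allocation as it is and label the adjusted analysis post hoc.

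Only if allocation has not started, the protocol could also replace "Simple random assignment" with a concealed, computer-generated list of permuted blocks of randomly varying size, stratified by two age bands. This is optional. It costs one sentence and a list; its downside is that, in an unmasked single-site trial, the last allocations in a block can sometimes be guessed. Varying block sizes and concealment reduce that risk but do not remove it.

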## **Participants**

### **Inclusion Criteria:**

- Clinical diagnosis of ADHD

- Age 5–12 years
- Residing in Istanbul
- Caregiver PSI  $\geq 21$
- Caregiver age between 18–65 years

#### **Exclusion Criteria:**

- Additional diagnosis with ADHD
- Cardiopulmonary issue in last 3 months
- Prior musical instrument training
- Caregiver BDI  $\geq 31$

## **Intervention**

#### **Experimental Group:**

Music-Based Occupational Therapy - structured rhythmic, singing, and instrument-based (harmonica, drum) sessions designed to improve self-regulation and executive functions.

#### **Control Group:**

Standard occupational therapy sessions emphasizing sensory-motor and behavioral regulation without musical elements.

## **Outcome Measures**

#### **Primary Outcome:**

- Change in attention (DSM-V Level 2 Inattention Scale)

#### **Secondary Outcomes:**

- Executive Function (Childhood Executive Function Inventory)
- Caregiver Burden (Zarit Burden Scale)

All measures assessed pre- and post-intervention.

## **Data Analysis Plan**

The analyses were performed using SPSS 25.0 software. For descriptive statistics, mean, standard deviation, and percentage values were used. Normal distribution was checked with the Kolmogorov-Smirnov Test. For independent variables, nominal data were evaluated with the Chi-Square Test, while numerical data were assessed with the T-Test / Mann-Whitney U Test. Two-Way Repeated Measures ANOVA was applied for within-group and between-group time interactions. The significance level for all tests was accepted as  $p < 0.05$ .

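### The plan names three ways to compare the arms without saying which is primary for the inattention score or what the normality check decides; one baseline-adjusted model would settle this and be more precise.

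*Combined protocol and SAP*

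**What the plan says.** All the analysis text is in one paragraph, the Data Analysis Plan of the combined protocol and SAP.

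- Normality: "Normal distribution was checked with the Kolmogorov-Smirnov Test". The variable, the level (each arm, pooled or residuals), the cut-off and the consequence of failing are not given.
- Two-sample tests: the sentence opens "For independent variables, nominal data were evaluated with the Chi-Square Test" and continues that "numerical data were assessed with the T-Test / Mann-Whitney U Test". No rule for choosing between the two is written.
- Change over time: "Two-Way Repeated Measures ANOVA was applied for within-group and between-group time interactions". No alternative is given for non-normal data.
- One threshold, p < 0.05, applies to every test.

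Under Outcome Measures, the primary outcome is change on the inattention scale. Executive function and caregiver burden are secondary. "All measures assessed pre- and post-intervention", so there are two time points. Under Groups, allocation is "Simple random assignment" to two arms. The documents give no sample size, SD or pre-post correlation, and name no effect estimate to be reported.

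**The concern.** A reader cannot tell which result answers the primary question. The scope of the two-sample tests turns on the words about independent variables, and these can be read in two ways.

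- **Independent-group comparisons, including the scale scores.** Each scale then has three candidate between-group tests: t-test, Mann-Whitney and ANOVA interaction. A normality check beside two alternatives suggests that the data choose between them. The quantity compared would change too, from a difference in means to a comparison of ranks.
- **Sample characteristics only.** The ANOVA is then the sole outcome analysis. It is still not named as primary, has no stated effect estimate, and uses the baseline score less efficiently than a covariate-adjusted model.

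At stake are an unambiguous primary result and some precision. A large inflation of false positives is not at stake.

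**Working it through.** The plan has no figure to reproduce. Inputs from the documents: alpha 0.05, two arms, two assessments, primary outcome defined as change. Assumptions: two-sided tests, 1:1 allocation, 10 to 50 children per arm, skewness 0.5 to 2.0, a true effect of 0.8 SD where power is quoted, and pre-post correlation r of 0.5 or 0.7.

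**1. What the ANOVA interaction tests.** Write D = post − pre for each child. With two time points, the group-by-time contrast is mean(D) in the music arm minus mean(D) in the control arm, and its error term is the pooled variance of D. Hence F(1, N − 2) = t², where t is the pooled two-sample t statistic on D. A numerical check confirmed the identity. A t-test on change therefore repeats the ANOVA interaction, whereas a Mann-Whitney test on change may contradict it.

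**2. Cost of choosing the test by the normality result.** The simulated rule was Mann-Whitney if either arm fails Kolmogorov-Smirnov (Lilliefors critical values), otherwise the t-test, with 20,000 trials per cell. Type I error across all cells:

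| Strategy | Type I error |
|---|---|
| t-test fixed in advance | 0.044–0.052 |
| Mann-Whitney fixed in advance | 0.042–0.052 |
| Chosen by the normality check | 0.048–0.058 |

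The gated rule costs about one percentage point at most. Reporting whichever test is significant would give about 6–7% at 20 per arm, but the plan does not describe that practice.

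**3. How often the tests disagree.** With no true effect, the t-test and Mann-Whitney differ on significance in about 2–4% of trials. With a 0.8 SD effect and 20 per arm, they differ in about 7% of normal data sets and 12–18% of skewed ones. By step 1, these rates also apply to Mann-Whitney on change against the ANOVA interaction.

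**4. Precision of the change-score comparison.** Let pre and post have the same variance σ² and correlation r.

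- Change score: Var(D) = 2σ²(1 − r).
- Baseline-adjusted post score: residual variance = σ²(1 − r²).
- Ratio: (1 − r²) / [2(1 − r)] = (1 + r)/2.

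At r = 0.5 the ratio is 0.75 (25% lower). At r = 0.7 it is 0.85 (15% lower). Confidence intervals narrow by the square root: √0.75 = 0.87 and √0.85 = 0.92, or about 13% and 8%.

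The ratio ignores the cost of estimating the slope. For a normal baseline this multiplies the variance of the adjusted difference by 1 + 1/(N − 4). At an assumed N = 40 that is 1 + 1/36 = 1.028, so the ratios become 0.75 × 1.028 = 0.77 and 0.85 × 1.028 = 0.87. Most of the gain remains.

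**The case against.** The strongest reply is that the plan already has one fixed outcome test. Change between arms is assigned to the ANOVA, and the normality check does not gate it. No outcome is nominal, so the chi-square half of the sentence fits participant characteristics, and the t-test / Mann-Whitney half plausibly does too. This is a fair reading and it stands as a possibility. It does not make the ANOVA the declared primary analysis, supply an effect estimate, or remove the loss of precision in step 4.

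Two stronger readings are tempting, and the documents support neither.

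- **That Kolmogorov-Smirnov steers the between-group test.** The plan never says so. It reports a check and, separately, lists two tests. Steering is a reasonable inference, but the missing rule is the firmer defect.
- **That the check misses most skew in small groups.** No group size is given, so small is an assumption. The result also depends on the degree of skew and the version of the test. At an assumed 20 per arm, the Lilliefors version flags a single arm with probability 0.19, 0.37 and 0.58 at skewness 1.0, 1.5 and 2.0. If either arm failing is enough, the figures are 0.34, 0.60 and 0.83. The uncorrected version flags 0.002, 0.01 and 0.04. The plan does not say which version was used.

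Gating is also not shown to be harmful throughout. At 20 per arm, skewness 1.5 and a 0.8 SD shift, the gated rule has power 0.79, against 0.70 for the t-test alone.

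Finally, replacing ANOVA with ANCOVA does not follow from any fault in a normality pre-test. That is correct: the case for ANCOVA rests on step 4, and removing the choice of test is an added benefit.

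**Conclusion.** The point holds as one of under-specification and avoidable imprecision, and it is a desirable improvement rather than a serious flaw. The plan does not name the primary analysis of the inattention score, the variables that receive a t-test or Mann-Whitney test, or the rule for choosing between them. That much rests on the text alone.

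If those tests cover the scale scores, strict gating keeps type I error at about 5–6%. The practical risk is conflicting results on the same scale. The precision gain from baseline adjustment applies under either reading of the plan, with its size depending on the assumed equal variances and correlation. All simulated figures depend on assumed group sizes and distributions.

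**What to change.** Name one primary between-group analysis for the inattention scale, to be used whatever a normality test shows: post-intervention score regressed on arm with the baseline score as covariate, reporting the adjusted difference with 95% CI. Use the same model for the executive function and caregiver burden scales. Inspect residuals descriptively. Specify one sensitivity analysis in advance, a permutation p-value or a bootstrap interval. Limit the t-test, Mann-Whitney and chi-square tests to describing the sample, and say so.

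The cost is a few sentences and a few lines of code, since the pre scores are already collected. There are two downsides.

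- Under marked skew, a rank test can have more power. Among unadjusted tests, the figures are 0.82 for Mann-Whitney and 0.70 for the t-test at an assumed 20 per arm, skewness 1.5 and a 0.8 SD shift. The fixed sensitivity analysis protects validity under skew but need not recover that power.
- The Data Analysis Plan is written in the past tense. If outcomes have already been analysed, report the model as specified afterwards, alongside the tests and selection rule actually used.

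### The pre/post group-by-time ANOVA is valid but leaves the baseline score unused as a covariate; ANCOVA would usually be more precise at almost no cost

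*Combined protocol and SAP*

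**What the plan says.** Study Design describes two parallel arms, and the Groups section gives the allocation as "Simple random assignment" with no stratification. The primary outcome is change in the inattention scale; the secondary outcomes are executive function and caregiver burden. Outcome Measures adds: "All measures assessed pre- and post-intervention". A baseline value of every outcome is therefore planned for every child.

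For comparing change between arms, the Data Analysis Plan offers one method: "Two-Way Repeated Measures ANOVA was applied for within-group and between-group time interactions". It names no covariate. The other between-group method, "numerical data were assessed with the T-Test / Mann-Whitney U Test", is also unadjusted. The plan does not say which test is primary. The interaction is read here as the test of the treatment effect because it is the only listed analysis that compares change between the arms. The documents state no sample size, power, effect size, SD or pre-post correlation.

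**The concern.** With only two time points, the group-by-time interaction compares mean change between the arms. That subtracts the whole baseline score from each child's post score, a slope of 1. Unless the true slope of post on pre is 1, this is not the best use of the baseline. If the slope is lower, the change score over-corrects: an arm that happens to start worse will appear to improve more. Randomisation makes the baseline difference zero on average, but nothing in the plan stratifies on or adjusts for the baseline score, so whatever difference arises in this one trial partly carries into the estimate.

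At stake is precision: a wider confidence interval and lower power from the same children. Bias over repeated randomisations and type I error are not at issue.

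**Working it through.** The plan gives no figure to reproduce.

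**Inputs from the documents:** two parallel arms, simple randomisation, one pre and one post measurement, group-by-time ANOVA without a covariate, significance level 0.05.

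**Assumptions:** ρ (pre-post correlation) from 0.3 to 0.9; k (post SD / pre SD) of 1, 1.25 or 0.8; equal arms of n = 20 or 15; a true effect of 0.8 SD for power.

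**1. Equivalence.** For two groups and two times, interaction F = (change-score t)². In a simulated dataset with 15 per arm, both equalled 3.1216.

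**2. Large-sample variances** (pre SD = 1):
- change score: k² + 1 − 2ρk
- ANCOVA: k²(1 − ρ²)
- information lost by the change score: (1 − ρk)² / (k² + 1 − 2ρk)

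At k = 1 the variances are 2(1 − ρ) and (1 − ρ)(1 + ρ). Their ratio is (1 + ρ)/2 and the loss is (1 − ρ)/2.

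**3. Cost of estimating the slope.** ANCOVA variance is multiplied by 1 + 1/(2n − 4): 1 + 1/36 = 1.028 at n = 20 and 1 + 1/26 = 1.038 at n = 15. Example at ρ = 0.5, n = 20: net loss = 1 − 0.75 × 1.028 = 0.229.

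**4. Confidence interval half-width** = t × √[(2/n) × variance]. At ρ = 0.5, n = 20:
- change score: 2.024 × √(0.1 × 1.0) = 0.64 SD
- ANCOVA: 2.026 × √(0.1 × 0.75 × 1.028) = 0.56 SD

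**5. Chance imbalance.** Given a baseline difference D, the change-score estimate is shifted by (1 − ρ)D in size when k = 1. One standard error of D at n = 20 is √(2/20) = 0.316 SD.

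Results for equal SDs (paired entries are change score vs ANCOVA):

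| ρ | Loss, large samples | Net loss, n = 20 | Net loss, n = 15 | 95% CI half-width (SD), n = 20 | Power for 0.8 SD, n = 20 | Shift from one-SE imbalance (SD), n = 20 |
|---|---|---|---|---|---|---|
| 0.3 | 35% | 33% | 33% | 0.76 vs 0.62 | 0.549 vs 0.722 | 0.22 |
| 0.5 | 25% | 23% | 22% | 0.64 vs 0.56 | 0.693 vs 0.802 | 0.16 |
| 0.7 | 15% | 13% | 12% | 0.50 vs 0.46 | 0.889 vs 0.925 | 0.09 |
| 0.9 | 5% | 2% | 1% | 0.29 vs 0.28 | no difference | 0.03 |

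Power uses the noncentral t with 2n − 2 and 2n − 3 degrees of freedom, averaged over random imbalance for ANCOVA. Simulation agreed.

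**6. Unequal SDs, large samples**, at ρ = 0.3, 0.5, 0.7, 0.9:
- k = 1.25: loss 22%, 11%, 2%, 5%
- k = 0.8: loss 50%, 43%, 37%, 39%

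**7. Where the gain disappears.** The large-sample loss is zero only when the slope ρk is 1. There ANCOVA pays the factor in step 3 for nothing: 2.8% at n = 20, 3.8% at n = 15. In small samples this extends to slopes near 1. At k = 1.25, ρ = 0.7 (slope 0.875), the ANCOVA/change variance ratio is 1.008 at n = 20 and 1.018 at n = 15. With equal SDs, the break-even at n = 20 is ρ = 2/1.028 − 1 ≈ 0.95.

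**8. Validity.** Over 10 to 30 per arm, simulated type I error was 0.047 to 0.051 for the change score and 0.049 to 0.053 for ANCOVA. At n = 20, both estimators averaged 0.80 for a true effect of 0.80.

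**The case against.** The strongest reply is that nothing is wrong. The primary outcome is defined as change, the planned test compares change, and that test is valid. The choice is between two legitimate estimators, and every figure above rests on assumed values that the documents cannot confirm; the loss could be 50% or about zero. In small samples with a slope near 1, ANCOVA is slightly worse. The Data Analysis Plan is also in the past tense ("The analyses were performed using SPSS 25.0 software"). If results are already known, swapping the primary test would be a data-dependent change.

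Most of this is true, and it limits the point to a recommendation. It does not remove it:
- The downside is small (about 3% of variance at 20 per arm, 4% at 15), while the upside is 13% to 33% at 20 per arm for ρ from 0.7 down to 0.3 with equal SDs.
- The outcome definition need not change. Regressing change on group and baseline gives the same group coefficient as regressing the post score on group and baseline.
- The past tense decides how the ANCOVA should be presented, not whether it is worth reporting.
- Simple randomisation is not itself a fault. Blocking on arm size alone would not balance baseline scores either. The case rests on the unused covariate.

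**Conclusion.** The point holds as an efficiency improvement that should be made, not as an error of validity. The planned interaction test is an unadjusted change-score comparison, and adjusting for the baseline score would usually give a more precise estimate. The existence of the large-sample loss (whenever the slope differs from 1) is certain. Its size here is not, because ρ, the SDs and the sample size are not stated. A low or moderate pre-post correlation, or a post SD smaller than the pre SD, makes the loss substantial; a slope near 1 makes it negligible or slightly reverses it in small samples.

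**What to change.** Add to the Data Analysis Plan wording such as:

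> The primary analysis is an ANCOVA of the post-intervention DSM-V Level 2 Inattention score on randomised group, adjusted for the pre-intervention score on the same scale, and reported as an adjusted mean difference with 95% confidence interval. The same model is used for the executive function and Zarit scores. The repeated-measures ANOVA is a sensitivity analysis.

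This also settles which test is primary and gives an effect estimate with its interval, where the plan now lists tests and a p-value threshold.

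Which route applies depends on timing, which the documents leave open:
- **Not yet analysed:** adopt the wording above.
- **Already analysed:** keep the planned test in place, report the ANCOVA beside it, and state when and why it was added.

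The cost is one degree of freedom and one sentence, with the same data, the same software and no additional children. In the second case there is also the disclosure that the ANCOVA is post hoc.

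### The pre/post repeated measures ANOVA uses only children with both scores and no as-randomised analysis set is stated; a baseline-conditional model would be more precise and would remove bias from baseline-dependent loss

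*Combined protocol and SAP*

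**What the plan says.** The primary outcome is "Change in attention (DSM-V Level 2 Inattention Scale"), and the Outcome Measures section adds "All measures assessed pre- and post-intervention". Each child therefore has at most two scores per scale. Under Study Design, allocation is "Simple random assignment", masking is "None (Open Label"), and treatment runs for "6 weeks, 1 session per week, 45 minutes each".

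The Data Analysis Plan opens with "The analyses were performed using SPSS 25.0 software". Its one model for comparing the arms over time is in the sentence "Two-Way Repeated Measures ANOVA was applied for within-group and between-group time interactions". It also says that "numerical data were assessed with the T-Test / Mann-Whitney U Test", but ties this to independent variables, so it is not clearly an outcome analysis. Those tests also use observed values only.

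The document does not state an analysis population, a missing-data method, a sample size or an expected dropout. It does not say that children are analysed in the arm to which they were randomised.

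**The concern.** A conventional repeated measures ANOVA needs a complete set of scores for each child. A randomised child with no post score is deleted, and the baseline goes too. If that happens, the analysis compares the children who stayed, and randomisation protects that comparison only when staying is unrelated to prognosis or is related to it in the same way in both arms.

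Families know their arm, the sessions differ visibly in content, and the plan expects music to do better, so unequal loss is plausible. If it occurred and was related to severity or to response, the estimated effect on attention would mix treatment with selection, and the 5% level would not hold. A second cost arises even with complete data: a change-score analysis makes less efficient use of the baseline than a baseline-conditional one.

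**Working it through.** **Inputs from the document:** two arms, two assessments, repeated measures ANOVA, significance level 0.05 (sidedness not stated; taken as two-sided). There is no sample size, power or dropout figure to reproduce.

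**Assumptions, not from the document:** 20 children per arm, scores with SD 1 where higher is worse, pre-post correlation r between 0.4 and 0.6, no true effect, and 10-25% loss in one arm. Biases are music minus control with the loss in the music arm, so negative favours music.

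**Step 1: what the planned test is.** On one simulated data set of 20 per arm, the arm-by-time F was 0.03330 and the squared t on change scores was 0.03330. They are the same test, so a child without a post score contributes nothing.

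**Step 2: precision with no loss or random loss.** The variance of a change score is 2(1 - r). The residual variance given baseline is 1 - r². The ratio of standard errors is √[(1 - r²)/(2(1 - r))] = √[(1 + r)/2].

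- r = 0.4: √0.70 = 0.84, a standard error 16% smaller
- r = 0.6: √0.80 = 0.89, 11% smaller

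These are large-sample values. In simulation, which pays for estimating the slope in a small trial, the reduction was roughly 7-15%. Under random loss both analyses had bias near 0 and type I error near 5%.

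**Step 3: loss that depends on baseline, in one arm.** If the retained children's mean baseline shifts by δ, their expected change shifts by (r - 1)δ. Losing milder children at 25% gave a simulated change-score bias of about -0.15 SD at r = 0.4, so δ = 0.15/0.6 = 0.25. The same δ at r = 0.6 gives -0.4 × 0.25 = -0.10 SD, which is what the simulation found. Losing severe children instead reverses the sign (+0.13 to +0.16 SD at r = 0.4, depending on how strongly severity drives loss). Two-sided type I error was about 6-7%. Conditioning on baseline brought the bias to about 0.

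**Step 4: loss that depends on lack of improvement, in one arm, r = 0.5.**

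| Loss | Analysis | Bias (SD) | False positives favouring music (nominal 2.5%) |
|---|---|---|---|
| 25% | change score | -0.25 | 10.5% |
| 25% | conditional on baseline | -0.20 | 9.0% |
| 10% | change score | -0.09 | 4.1% |

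The share left after conditioning is 0.20/0.25 = 0.80 here. Other selection strengths gave 0.16/0.21 = 0.76 and 0.25/0.32 = 0.78. The false-positive rate at 25% loss ranged from about 9% to 16% with the strength of selection, which is itself an assumption.

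**Step 5: loss that depends on the post score itself.** With 20 or 30 per arm, r = 0.5 and 10-30% lost in each arm (poor post scores in one arm, at random in the other), change scores had bias -0.06 to -0.18 SD and type I error 6-9%. Conditioning on baseline had bias -0.10 to -0.27 SD and type I error 7-18%. Here the baseline-conditional analysis does worse.

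**The case against.** The strongest reply is that the harm is conditional. The document reports no dropout, treatment is six weekly sessions, and the control is active occupational therapy. With complete data the repeated measures ANOVA is a valid test. Deletion of incomplete cases is a property of the procedure, not something the plan declares. All of this stands.

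A reader might infer that the comparison is already completers-only, that randomisation has been lost, or that the result is tilted towards music. The document supports none of these. It does not show that any post score is missing. An open label makes unequal loss possible but does not demonstrate it, and the direction of bias depends on who leaves.

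A second reply is that a different model does not repair the worst case. That also stands. With only two assessments, a child without a post score adds almost nothing to the treatment contrast in a mixed model, so the result is close to baseline-adjusted analysis of completers. It handles loss explained by baseline; Steps 4 and 5 show that it does not handle loss tied to response. Obtaining post scores from children who stop sessions would do more, but the plan is written in the past tense and that may no longer be possible.

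What the replies do not remove is the missing statement of who is analysed and in which arm, and the gain in precision, which does not depend on any loss.

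**Conclusion.** The point holds as a cheap improvement, not as a demonstrated bias. The document establishes that the only arm-by-time model is a change-score test in children with both scores, and that no as-randomised analysis set or missing-data method is given.

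The size of any bias is unknown because loss is not reported. Under the assumptions above it is about 0.10 to 0.15 SD in either direction for 25% baseline-dependent loss in one arm, and conditioning on baseline removes it. For loss driven by lack of improvement it is about -0.1 to -0.25 SD at 10-25% loss, of which about three quarters remains. If loss is absent or random, the only gain is a standard error roughly 7-15% smaller.

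**What to change.** Replace the repeated measures ANOVA sentence with:

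> Each outcome is analysed with a linear mixed model (SPSS MIXED) with time and arm-by-time, a common baseline mean and unstructured covariance, including every randomised child in the arm assigned, regardless of sessions attended, with all available scores.

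To obtain the common baseline mean, enter arm-by-time as a single indicator for a music-arm post score, with no main effect of arm.

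Then:

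- State that this handles loss that depends on baseline only.
- Report the numbers randomised and analysed in each arm, so that a reader can see whether the problem arose.
- For the primary outcome, add one sensitivity analysis that imputes missing music-arm post scores as no change from baseline or as in the control arm. Present it as a probe of outcome-dependent loss, not a correction: in simulation with 25% loss of non-improvers, no-change imputation only reduced the bias from between -0.22 and -0.32 SD to between -0.16 and -0.24 SD.

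The cost is one paragraph, one extra table and a slightly less familiar model. No new data are needed, the procedure is in the software already named, and it can be run as a re-analysis if the planned one is complete.
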